Subjects will receive compensation for their time and effort at the completion of each clinic visit beginning with the 6 week follow-up.

Data and Safety Monitoring: The first three subjects will be enrolled at a rate of no more than one subject per week. After review of the 7 day safety data for each of the first 3 subjects, the Safety Review Committee (SRC) will recommend either to open enrollment for the remaining subjects or to discontinue enrollment. The SRC will review the occurrence of AEs weekly, with 24 hour reporting for SAEs. Stopping rules will be defined in the protocol.

Monitored Parameters:

Safety:

- Hematology, blood chemistry, urinalysis
- Vital signs and physical assessments
- Unsolicited and solicited adverse events (clinic visits, diary cards and telephone contacts)
- Follow-up safety surveillance through 2 years

Bone Regeneration:

- CT analysis

Endpoints:

Safety:

- Incidence of local adverse events including ectopic bone formation if any
- Incidence of systemic adverse events
- Incidence of changes to laboratory parameters relative to baseline values

Bone Regeneration:

- The proportion of subjects at Day 42 and 180 and 360 with evidence of mineralized bone regeneration at the site of the original cranial defect relative to baseline (Day 0)
- The percentage of bone regeneration in the original cranial defect at Day 42 and 180 and 360 relative to 0% at baseline (Day 0)

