An additional concern is that InFuse® only allows the placement of a sponge which retains the rhBMP-2 for a very short period of time and has very little structural integrity or adaptability for irregular wounds. The B-247 Cranial Bone Graft Implant overcomes each of these shortcomings. First, the TCP crystals tightly bind and gradually release the pln.247-pBI plasmid and the rhBMP-2 so the risk of local seroma or systemic toxicity within 3 days after placement are reduced. Second, the cross-linked gelatin scaffold retains the crystals so the biologicals remain where placed. Third, the cross-linked gelatin scaffold allows the graft to be molded into the wound and is adaptable to irregular wounds. Fourth, the cross-linked gelatin scaffold is not a putty, as used by Stryker, but is a porous scaffold for immediate cell infiltration.

The clinical objective is to grow new bone where bone has been lost. In doing so, the **first requirement** is that space must be filled with a material (liquid, gel, solid, particles, or porous polymer) that allows/promotes cellular infiltration immediately. The **second requirement** is that the material should retain and protect the biologics (growth factor and co-activator) from pre-mature release in the first few days since the early wound is highly inflammatory. The material should gradually release the majority of biologic load between 4 and 14 days for most effect during the beginning of the regenerative phase.

The B-247 Cranial Bone Graft Implant generates a heparan sulfate proteoglycan that tightly binds FGF-2 or BMP-2 (1 nM estimated kD) and significantly augments BMP activity in an osteoblast mineralization assay (or FGF-2 in a proliferation assay). Classic growth factor/receptor interaction mechanisms suggest that the heparan sulfate chains co-activate growth factors by promoting receptor dimerization through binding interactions between the growth factors and the glycosaminoglycans.

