7. STUDY DESIGN

7.1 Study Overview

This is a single center, unblinded, safety and efficacy study.

A total of 12 subjects will be enrolled.

All 12 subjects will receive the B-247 Cranial Bone Graft Implant.

Enrollment will begin with 3 subjects enrolled at a rate of no more than one subject per week. The second, and third subjects will only be treated with the experimental device if stopping rules (see Section 14.3) are not met and other safety concerns are absent. Following review of Day 7 safety data for each of the first 3 subjects, the SRC will determine whether to open enrollment to the remaining 9 subjects or to discontinue enrollment. The SRC will review the occurrence of AEs weekly, with 24 hour reporting for SAEs. Stopping rules are described in full in Section 14.3.

Safety will be assessed in all participants. Each participant will be requested to record solicited AEs daily for 2 years after their device placement using study diary cards. Additionally, unsolicited adverse events will be collected immediately following surgical device placement through two years via telephone contacts and at clinic visits. Serious adverse events (SAEs) will be collected throughout the 2 year period of safety surveillance.

Safety evaluation will include hematologic and biochemical toxicity evaluation.

Blood and urine samples will be collected at screening (Day -21 to -1), on Day 0 prior to administration of the device, and again on Days 7, and 42 to measure the effects of device on blood chemistry, urinalysis, and hematology. The urine and blood samples obtained on Day 0 will be used for the baseline comparison.

Subjects will be asked to undergo a physical examination at screening (Day -21 to -1) and a physical assessment including vital signs, lymph node exam, and symptom directed exams at all clinic visits following enrollment (Days 0, 3, 7, 42, 180, and 1 year).

Telephone contacts will occur on the first two days after surgery (Days 1, 2) for study staff follow-up on possible adverse events. In addition, telephone contacts will be made after two years to document the occurrence of SAEs and the resolution of AEs ongoing at the one-year visit.

The overall safety assessment of the device will be based on the incidence of local and systemic reactogenicity, the incidence of changes to laboratory parameters relative to baseline values, and solicited and unsolicited adverse events.

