9.1 Study Visits

Screening Visit (Day -21 to -1)

Participants will be screened for eligibility to participate in the study. The following procedures must be performed during the screening period:

- a. Obtain Informed Consent prior to any study procedures.
- b. Check eligibility criteria.
- c. Obtain medical history.
- d. Record concomitant medication
- e. Perform physical examination.
- f. Obtain blood samples (10 mL + 5 mL) for screening clinical laboratory assessments.
- g. Obtain a blood sample (4 mL) for HIV serology and illicit drug screen.
- h. Obtain CT image of cranial defect.

Visit 1 (Day 0, Baseline)

- a. Confirm that the subject wishes to remain in the trial.
- i. Confirm eligibility criteria as needed.
- j. Obtain interim medical history as needed.
- k. Record concomitant medication as needed.
- l. Perform physical assessment as needed.
- m. Obtain blood samples (10 mL + 5 mL) and urine sample for clinical laboratory assessments if more than 3 days since prior screening.
- n. Obtain blood sample (4 mL) for PT and PTT tests if more than 3 days since prior screening.
- o. Administer experimental device.
- p. Keep the subject under observation for 30 minutes post administration and record any reaction in the source documents and CRF.
- q. Give participant the diary card with instructions for use.
- r. Record AEs and SAEs.
- s. Set up appointment for Visit 2 (Day 3).

Contact 1 (Day 1)

- a. Record symptoms and symptom severity on Telephone Contact Symptom Assessment Form.
- b. Record AEs and SAEs.
- c. Schedule in-clinic evaluation for moderate or severe AEs or SAEs, as clinically appropriate.

Contact 2 (Day 2)

- a. Record symptoms and symptom severity on Telephone Contact Symptom Assessment Form (Appendix D).
- b. Record AEs and SAEs.
- c. Schedule in-clinic evaluation for moderate or severe AEs or SAEs, as clinically appropriate.

Visit 2 (Day 3)

- a. Confirm that the subject wishes to remain in the trial.
- b. Obtain interim medical history.
- c. Review diary card with subject.
- d. Record concomitant medication.
- e. Perform physical assessment (vital signs, lymph node exam, and symptom directed exam).
- f. Record AEs and SAEs.
- g. Set up appointment for Visit 3 (Day 7).

Visit 3 (Day 7)

- a. Confirm that the subject wishes to remain in the trial.
- b. Obtain interim medical history.
- c. Record concomitant medication.

- d. Perform physical assessment (vital signs, lymph node exam, and symptom directed exam).

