11.1.2 Solicited Local and Systemic Events

All subjects will be given diary cards that are to be filled out for the purposes of recording any changes in health status after device administration.

- Diary Card #1 will be used to record all local and systemic events, as well as any other AEs that represent a change in the health status of the subject, from device placement through Visit 3 (Day 7).
- Diary Card #2 will be used to record unsolicited adverse events and SAEs through Visit 4 (Day 42).
- Diary Card #3 will be used to record unsolicited adverse events and SAEs after Visit 4 (Day 42) through Visit 5 (Day 180).
- Diary Card #4 will be used to record unsolicited adverse events and SAEs after Visit 5 (Day 180) through Visit 6 (Day 360).
- Diary Card #5 will be used to record unsolicited adverse events and SAEs after Visit 5 (Day 360) through Contact #3 (Day 720).

The diary cards will be considered the source document and will be transcribed into the case report form (CRF) by study site personnel. If the diary card is lost, this will be documented in the CRF, and the limited information collected during the clinic visit will serve as the source document. All other data points will be noted with "ND" (not determined).

For the purpose of collecting solicited local and systemic events, the following procedures will be implemented:

1. Study participants will be supplied with a digital thermometer on day 7 and shown how to use it to measure their oral temperature for weeks 1-6 following administration of the study product.
2. Participants will be asked to observe for AEs daily during the first 6 weeks post-implantation period. This includes systemic events including fever, chills, nausea/vomiting, weakness, muscle pain, and headache.
3. Diary Card #1 will be distributed during Visit 1 (Day 0) and collected during Visit 3 (Day 7). Diary Card #2 will be distributed during Visit 3 (Day 7) and collected during Visit 4 (Day 42). Diary Card #3 will be distributed during Visit 4 (Day 42) and collected during Visit 5 (Day 180). Diary Card #4 will be distributed during Visit 5 (Day 180) and collected during Visit 6 (Day 360). Diary Card #5 will be distributed during Visit 6 (Day 360) and collected by mail at Contact #3 (Day 720). Subjects will be asked

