13.2 Variables and Timepoints of Measurement

13.2.1 Safety Variables

In-clinic safety evaluation on Days 0, 3, 7, 42, 180, and 360 will be graded for severity and relationship to the study agents and will include:

- a) Rates of SAEs and their relationship to device placement, through 2 years of long-term follow-up.
- b) Rates of local or systemic solicited AEs and their categories (mild, moderate and severe), through Day 360 ± 28 days.
- c) Rates of reported unsolicited AEs, through Day 360 ± 28 days.
- d) Hematologic and biochemical toxicity evaluation following device placement.

Osteogenicity will be evaluated using radiographs and CT scans obtained from participants on Day 0 (baseline, pre-implantation), Day 42 (± 7), 6 weeks after device placement), and Day 180 (± 14) 6 months after device placement).

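### Solicited local adverse events are promised as a safety rate through Day 360, but no cranial-site event is named, the diary cards turn to unsolicited events after Day 7, and no graft-site inspection is a fixed visit item

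*Protocol*

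**What the plan says.** Safety is the primary objective (Section 6.1). The first safety endpoint in the synopsis is "Incidence of local adverse events including ectopic bone formation if any". Section 13.2.1(b) lists "Rates of local or systemic solicited AEs and their categories", through Day 360 with a 28-day window.

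Section 11.1.2 introduces its collection steps with "For the purpose of collecting solicited local and systemic events, the following procedures will be implemented". Item 2 asks subjects to look for AEs daily for the first six weeks and adds: "This includes systemic events including fever, chills, nausea/vomiting, weakness, muscle pain, and headache". No event at the cranial site is named there or elsewhere as a solicited term. On the cards, the section says "Diary Card #1 will be used to record all local and systemic events, as well as any other AEs", and this runs from placement to Day 7. Cards #2 to #5, covering Day 7 to Day 720, are described as recording unsolicited events and SAEs.

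For the visits, Section 7.1 specifies a "physical assessment including vital signs, lymph node exam, and symptom directed exams at all clinic visits following enrollment". The Section 3 schedule reduces this to vital signs and a node check, and Section 9.1 repeats the three-part wording for Visits 2 to 6.

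**The concern.** A solicited rate needs a fixed list of events, a fixed period and an instrument that asks. For local events the protocol states no list, and after Day 7 the described cards are not instruments for solicited events. The visit examination does not clearly make up for this: in a subject without complaints, nothing requires anyone to look at the graft site or do a neurological check.

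What gets recorded at the site may then depend on what the subject mentions and on each examiner's habits. That matters for the local AE endpoint. It also matters for the Section 14.3 rule triggered by three or more related moderate events of one type, because that count needs consistent terms and consistent looking. A statistical analysis plan cannot repair this later, since it cannot recover data that were not collected.

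**Working it through.** **1. What is collected, by interval** (Sections 3, 7.1, 9.1 and 11.1.2)

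| Interval | Card and its stated use | Local term named | Fixed exam items | CT after placement |
|---|---|---|---|---|
| Day 0 to 7 | #1: local, systemic and other AEs | none | vital signs, nodes (Days 0, 3, 7) | none |
| Day 7 to 42 | #2: unsolicited, SAEs | none | vital signs, nodes (Day 42) | Day 42 |
| Day 42 to 180 | #3: unsolicited, SAEs | none | vital signs, nodes (Day 180) | Day 180 |
| Day 180 to 360 | #4: unsolicited, SAEs | none | vital signs, nodes (Day 360) | Day 360 |
| Day 360 to 720 | #5: unsolicited, SAEs | none | none (telephone) | none |

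Section 13.2.1(b) needs solicited local data in the first four rows. Only the first row has a card that takes local events other than as unsolicited reports or SAEs, and even there no term is named.

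**2. The solicited period differs between sections.** Card #1 ends at Day 7. Item 2 of Section 11.1.2 has daily observation for six weeks. The synopsis (diary cards for one year) and Section 13.2.1(b) (Day 360) both imply about a year. Section 7.1 has daily solicited recording for two years. These are four different periods.

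**3. The plan's own detection figures.** Section 13.1 states a 90% chance of at least one SAE among 10 subjects at a true rate of 21%, and a 90% chance of none at 1%.
- 1 − 0.79^10 = 0.905, and 0.99^10 = 0.904. Both reproduce.
- At the planned 12 subjects: 1 − 0.79^12 = 0.941.

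These figures assume that every event is captured.

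**4. Illustration of incomplete capture.** Let s be the fraction of local events that is recorded. The protocol gives no value for s, so a range is shown. The 21% is borrowed from Section 13.1, where it refers to SAEs; it is not an estimate of local events. With n = 12:
- P(at least 1 recorded) = 1 − (1 − 0.21s)^12.
- P(3 or more subjects with a recorded event) is the upper binomial tail at rate 0.21s.
- The true rate needed for a 90% chance of at least one recorded event is (1 − 0.1^(1/12))/s = 0.175/s.

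| s (assumed) | P(at least 1) | P(3 or more) | True rate for 90% |
|---|---|---|---|
| 1 | 0.941 | 0.477 | 17.5% |
| 0.9 | 0.919 | 0.402 | 19.4% |
| 0.75 | 0.872 | 0.290 | 23.3% |
| 0.5 | 0.736 | 0.124 | 34.9% |
| 0.25 | 0.476 | 0.022 | 69.8% |

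The third column is only a rough analogue of the Section 14.3 rule, which also requires moderate grade, relatedness and a common type.

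**The case against.** The strongest reply is that local events have several other routes into the database.
- Card #1 takes all local events to Day 7, which covers the data used for the Safety Review Committee's decision after the first three subjects (Section 9.3).
- The synopsis provides in-hospital surveillance for seven days.
- Section 11.1.3 has AEs actively asked about at every contact and visit, with clinical records as source documents.
- CT at Days 42, 180 and 360 needs no complaint, directly serves the ectopic bone part of the endpoint, and is described in Section 8.1 as being for safety as well as efficacy.
- The six named symptoms read as examples. Section 11.1.2 shows that the cards carry specific questions, and neither the cards nor the telephone symptom form (cited in Section 9.1 as Appendix D) is in the document at hand. They may contain local prompts.

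Much of this stands. A reader might infer that local events are under-detected, or that no event at the site is ever prompted. The documents do not establish either: the first is an inference, and the second would need the forms.

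A reader might also infer from Section 5.3, which says the product binds its biologics "so the risk of local seroma or systemic toxicity within 3 days after placement are reduced", that this gap is what prevents the trial from testing a seroma advantage. It is not. That is a background comparison with a marketed product, and a single-arm study of 12 could not test it even with perfect collection. Nor do the documents give a basis for dropping the lymph node check.

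The reply does not close the gap. Card #1 names no local term and stops at Day 7. The seven-day surveillance sits badly with the telephone contacts on Days 1 and 2 and the appointment made for Day 3 in Section 9.1; those passages must be reconciled, and none of them specifies a site examination. The active questioning is general. No CT falls between placement and Day 42. And whatever the unseen forms contain, Sections 11.1.2 and 13.2.1(b) still disagree on whether solicited local events are collected after Day 7.

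**Conclusion.** The concern holds as a specification gap and an internal contradiction. Section 13.2.1(b) promises a solicited local AE rate through Day 360 that Section 11.1.2 leaves without terms throughout and without a solicited-event card after Day 7. Four different solicited periods are in play. Graft-site inspection is not a fixed item at any visit, so events not visible on CT may be captured incompletely and inconsistently, most plausibly after Day 7.

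The size of any loss cannot be derived from the protocol. The fall from 94% to 74% at half capture rests wholly on an assumed capture fraction and a borrowed 21% rate, and shows only how sensitive a 12-subject study would be. The conclusion on capture also assumes that the diary cards and telephone form add no local prompts beyond what Section 11.1.2 describes. The conflict over periods does not depend on that. The gap should be closed before enrolment, because missing observations cannot be restored at analysis.

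**What to change.** - In item 2 of Section 11.1.2 and on the diary cards, name local cranial-site events, for example swelling or fluid collection, redness, wound drainage or opening, and site pain.
- State one collection period for solicited events and bring the synopsis, Section 7.1, the card descriptions in Section 11.1.2 and Section 13.2.1(b) into line with it.
- In Section 7.1, the Section 3 schedule and Section 9.1 (Visits 2 to 6), make graft-site inspection and a brief neurological check fixed items, with or without symptoms, alongside the existing vital signs and node check.
- Report the solicited local AE rate in Section 13.2.1(b) on the named list.

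The cost is a few minutes at each visit already planned and a reprint of the cards. Reported local AE incidence will probably rise, which should be read as fuller capture.

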11.1.3 Unsolicited Adverse Events

All AEs and SAEs, including any condition that, according to the subject, represents a change in health status, and that occurs after the first administration of the study agent on Day 0 until the follow-up assessment at Contact #3 (Day 720) will be recorded. This information will be actively surveyed at every telephone contact or site visit with the subject during the period between Visit 1 and Contact #3. All SAEs that occur after the first administration of the study agent until the 2 year follow-up contact will be recorded. The source documents will be the subject diary cards, and the clinical records, from which AEs (as described above) will be transcribed to the CRF.

Any unresolved AE will be followed until its resolution or until the 24 month follow-up telephone contact, whichever occurs first.

11.1.4 Adverse Event Grading Scales

The severity of all adverse events will be graded as mild (Grade 1), moderate (Grade 2), severe (Grade 3), or potentially life threatening (Grade 4) according to the adverse event grading scale provided below. This grading scale will be used for local adverse events (those related to the cranial site of device administration) and systemic adverse events.

Mild (Grade 1)	Moderate (Grade 2)	Severe (Grade 3)	Potentially Life Threatening (Grade 4)
Symptom is present but does not interfere with activity	Symptom interferes with some activities but does not cause missed attendance at school or work	Incapacitating, unable to attend school or work or perform essential daily activities	Requires emergency room visit or hospitalization

Abnormal vital signs will be graded according to the above severity scale. This grading scale is based on the scale provided in the draft FDA guidance for industry, “Toxicity Grading Scale for Healthy Adult and Adolescent Volunteers Enrolled in Preventive Vaccine Clinical Trials” (April 2005).”

Any "severe" rating for local or systemic events requires the participant to call the study site for evaluation, the study site to notify the Medical Monitor (at the discretion of the investigator), and place comments on the AE page of the CRF that describe the event(s). Any severe adverse event that is deemed possibly, probably or definitely related to the study treatment will invoke a temporary stopping rule for the study to permit evaluation of the event by the SRC (see Section 14.3).

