- d. Verify telephone contact information and mailing address and provide instructions to participant in the event of a change in contact information.

Additional Clinic Visits

Any subject with an abnormal laboratory result or who experiences an adverse event may be requested to come into the clinic for additional follow-up evaluation not specified by the protocol if this is deemed medically prudent by the investigator.

9.2 *Obtaining, Handling, Storage, and Shipment of Specimens*

9.2.1 *Blood Samples for Safety Laboratory Tests*

Blood samples collected for safety analysis will be labeled and handled per the local reference laboratory standard operating procedures for hematology and biochemistry profiles. Blood samples for safety laboratory tests will include one 5 mL and one 10 mL sample, as well as one 4 mL sample for PT and PTT testing where specified.

9.2.2 *Urine Samples*

A clean-catch urine sample will be collected by each participant for safety evaluation. Study personnel will be responsible for instructing subjects on this technique. Urine samples will be handled and labeled per the local reference laboratory standard operating procedures for urinalysis.

9.3 *Safety Data Review*

The SRC will perform a review of the safety data through seven days post-administration for the first three subjects, and through seven days post-administration for all subsequent subjects. The SRC will use the following evaluation criteria to approve the completion of enrollment after the first 3 subjects:

- a) Absence of SAEs or severe AEs "definitely", "probably" or "possibly" related to the experimental device.
- b) No evidence of severe hematologic or biochemical toxicity.
- c) No consistent pattern of AEs that, in the judgment of the SRC, represents a significant threat to the safety of the subjects with continued enrollment.

Approval from Agenta will be obtained before proceeding with treatment of subjects 4-12.

9.4 *Compliance with Protocol*

All participants who receive the experimental device will be included in the safety evaluation.

The following events are to be considered sufficient reason for discontinuation of a participant from the study:

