14.3 Stopping Rules

Stopping rules will be in place to arrest the enrollment process and suspend all experimental device placement with the occurrence of significant safety event(s). The stopping rules are:

- Any SAE or severe AE that is definitely, probably, or possibly related to the experimental device in the opinion of the investigator or Safety Review Committee.
- Occurrence of 3 or more moderate AEs of the same type that are definitely, probably, or possibly related to the study agent in the opinion of the investigator or Safety Review Committee.

The occurrence of AEs and SAEs will be monitored by the Medical Monitor who will notify the other members of the SRC if a condition is met to institute a stop rule. Enrollment and study agent administration cannot continue after a stop rule has been implemented until the SRC has reviewed the AEs and other subject safety data and made a recommendation to continue the trial as planned, modify the protocol or stop enrollment. The recommendation of the SRC must be reviewed and approved by Agenta.

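### The moderate/severe boundary rests partly on missed school or work, which says little just after cranial surgery, yet the grade decides whether one or three related non-serious events pause enrolment.

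*Protocol*

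**What the plan says.** Section 11.1.4 gives one four-grade scale for all local and systemic adverse events. Grade 2 reads "Symptom interferes with some activities but does not cause missed attendance at school or work". Grade 3 reads "Incapacitating, unable to attend school or work or perform essential daily activities". The stated source is draft FDA guidance titled "Toxicity Grading Scale for Healthy Adult and Adolescent Volunteers Enrolled in Preventive Vaccine Clinical Trials". No rule says which grade applies when two could fit.

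The grade drives three actions:

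- **Stopping rules (section 14.3).** Enrolment and implantation are suspended by "Any SAE or severe AE that is definitely, probably, or possibly related to the experimental device", or by "Occurrence of 3 or more moderate AEs of the same type that are definitely, probably, or possibly related to the study agent".
- **Gate after three subjects (section 9.3).** "The SRC will perform a review of the safety data through seven days post-administration for the first three subjects". Criterion (a) is "Absence of SAEs or severe AEs" with a definite, probable or possible relation to the device. Criterion (c) is "No consistent pattern of AEs that, in the judgment of the SRC, represents a significant threat to the safety of the subjects".
- **Reporting (section 14.2).** Severe events reach the Medical Monitor within 24 hours, moderate and mild ones within 7 days.

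The subjects are trauma and craniotomy patients (section 2). The synopsis plans in-hospital surveillance for 7 days after implantation.

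**The concern.** Missed attendance is a real signal in a healthy volunteer who would otherwise be at work. In a man a few days out from cranial surgery it reflects the operation and the hospital stay, whatever the symptom. That is also the period reviewed at the section 9.3 gate.

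Grade 2 states causation: the symptom must not be what causes the absence. Grade 3 does not. It refers to being unable to attend and joins this to essential daily activities with the word or. A headache that limits only some activities is therefore Grade 2 if Grade 3 is read causally, but could be recorded as Grade 3 if it is read literally.

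The relatedness judgment does not remove the problem. The only relatedness scale given (section 10.2, written for SAEs) calls an event possibly related even when another cause may explain it, and possible relatedness counts under both stopping rules. The solicited systemic symptoms in section 11.1.2, such as headache, nausea and weakness, can also follow surgery. The grade is then what selects the one-event or the three-event rule.

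An error can go either way. Over-grading can pause the trial on one moderate event. Under-grading can miss the automatic stop, or delay it to the third event, and can lengthen reporting from 24 hours to 7 days. This matters more because section 5.5 reports no previous human experience with the plasmid component.

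**Working it through.** **The plan's own figures.** Section 13.1 gives a 90% chance of at least one SAE among 10 subjects at a true rate of 21%: 1 − 0.79^10 = 0.905. For a 1% rate it gives a 90% chance of none: 0.99^10 = 0.904. Both reproduce. They are not affected here, because a related SAE stops enrolment whatever its grade.

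**The grade cells side by side**, for a related, non-serious symptom limiting some activities in a subject off work because of surgery:

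| Reading of Grade 3 | Grade 2 met? | Grade 3 met? |
|---|---|---|
| Causal (the event prevents attendance) | Yes | No |
| Literal (the subject cannot attend) | Yes | Arguably yes |

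A symptom that is itself incapacitating, or that prevents essential daily activities, is Grade 3 on either reading. The ambiguity lies below that level.

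**How far apart the two rules are.** Let p be the per-subject rate of one type of related, non-serious event, at most one per subject. The protocol gives no such rate, so p is assumed. The chance of suspension is P(X ≥ 1) = 1 − (1 − p)^n if every event is graded severe, and P(X ≥ 3) if every event is graded moderate, with X binomial(n, p).

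| p | n = 12: severe / moderate | n = 3: severe / moderate |
|---|---|---|
| 10% | 72% / 11% | 27% / 0.1% |
| 20% | 93% / 44% | 49% / 0.8% |
| 30% | 99% / 75% | 66% / 2.7% |

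This contrasts all-severe with all-moderate grading. It shows what the grade controls, not the effect of the ambiguity.

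**Effect of grading errors.** Let k be the number of related, non-serious, same-type events, counted across subjects, with independent errors. Let m be the chance that a true Grade 2 is recorded as 3, and u the chance that a true Grade 3 is recorded as 2. Both are assumed.

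- Unneeded pause: m for k = 1; 1 − (1 − m)^2 for k = 2.
- Automatic stop missed: u for k = 1; u^2 for k = 2.

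| Assumed m or u | Pause, k = 1 | Pause, k = 2 | Missed, k = 1 | Missed, k = 2 |
|---|---|---|---|---|
| 10% | 10% | 19% | 10% | 1% |
| 25% | 25% | 44% | 25% | 6% |
| 50% | 50% | 75% | 50% | 25% |

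For k = 1 the output is simply the assumed input.

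For k ≥ 3 a stop occurs under either grade, but its timing can change. A stop due at the first severe event is delayed past it with chance u. It is delayed to the third event when the first two are both under-graded, with chance u^2 (1%, 6% or 25%).

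**The case against.** The strongest reply is that the scale grades the event, so its row should be read consistently. Grades 1 and 2 both speak of the symptom, and section 10 speaks of the intensity of a specific event. On that reading Grade 3 also means that the event causes the inability, and a symptom limiting some activities is plainly Grade 2. Grade 3 also opens with incapacitation, and what follows may only explain that word. This stands in part: the double grade needs a causal reading of Grade 2 and a literal one of Grade 3, and a careful investigator would probably avoid it. But the Grade 3 cell does not say so. Section 10 describes intensity as the patient perceives it, section 11.1.2 makes the diary card the source document, and section 11.1.4 has the participant call the site after a severe rating. The words must therefore work for patients too.

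The safeguards also stand. Over-grading leads to a temporary stop, after which the Safety Review Committee (SRC) may recommend continuing. Under-graded events still face section 9.3(c), Day 7 review of each subject and weekly SRC review, although section 14.2 lets a weekly meeting be cancelled if all members agree that there is nothing to discuss.

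A reader might infer that the scale is unusable, or that postoperative events generally meet both grades. The protocol does not support either: incapacitation and essential daily activities still separate most events. Nor is absence from work documented for every day of the gate window. It is inferred from the surgery and the planned 7-day stay, which fits poorly with telephone contacts on Days 1 and 2 and a Day 3 appointment. After discharge it is an assumption.

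**Conclusion.** The point holds as an ambiguity in a stated rule that feeds the stopping rules, and the wording should be changed. The attendance cue is uninformative early after cranial surgery, and Grade 3 omits causation. The consequence is confined to related, non-serious events. With one or two of the same type, the grade decides whether a section 14.3 stop occurs; with three or more, it decides when. A related event graded severe in the gate window also fails section 9.3(a).

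The size is unknown, because nothing in the protocol gives a misgrading frequency or an event rate. The error table is illustrative and assumes independent errors. The contrast of 72% with 11% at an assumed 10% event rate must not be read as the effect of the ambiguity. Expected harm is modest, given the usable anchors, the temporary stop, section 9.3(c) and weekly review. The correction is still worth making because it is cheap and the rule protects subjects in an early human trial.

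**What to change.** Drop the attendance wording from both grades in section 11.1.4 and state causation:

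- **Grade 2:** the event interferes with some activities but does not prevent essential daily or self-care activities.
- **Grade 3:** the event itself is incapacitating or prevents essential daily or self-care activities.
- **Tie-break:** when it is unclear whether the event or the surgery causes the restriction, assign the higher grade.

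Surgery also restricts self-care in the first days, so the replacement anchors are not free of the same problem. Explicit causation and the tie-break deal with it. Grading only what exceeds expected recovery should be avoided: that baseline is undefined and could encourage under-grading. Leave the relatedness judgment and the stopping rules unchanged.

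The cost is rewording one table and the matching CRF and diary guidance, slightly more clinical judgment, and possibly a few extra temporary pauses.
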